**Appendix B**

Study Subject Flowsheet	Enrollment - Day 1*	Days 3, 5, 7 & 9	Day 11	On Discharge
Informed Consent	x			
Entry Criteria	x			
Demographics	x			
Medical and Surgical History	x			
Prior & Concomitant Medications	x	x	x	x
Vital Sign Measurements	x	x	x	
ISTH DIC Score	x	x	x	
SOFA Score	x		x	
Blood Draw	x	x	x	
Urine or Serum Pregnancy Test if applicable	x			
Platelet	x	x	x	
PT, INR	x	x	x	
PTT	x	x	x	
Hemoglobin and Hematocrit	x	x	x	
Fibrinogen	x	x	x	
D-Dimer	x	x	x	
AT3 Level	x	x	x	
Anti-Xa	x	x	x	
Dosing if randomized to group with AT3 Infusion 	x 	x 		
Adverse Events 	x	x	x	x 
Hospital LOS				x
Mortality				x
PF ratio change				x
Days on Ventilator				x
Days on ECMO				x
VTE's				x
Bleeding Events				x

\*: Day refers to a 24 hour period.

x: To be completed

1: Only if randomized to AT3 Infusion and AT3 level is at specified level

2: Only Serious Adverse Events will be captured from last dose to hospital discharge.

### Appendix C

The Secondary endpoint measurements:

- a. D-dimer level change from baseline to Day 9 in mcg/mL FEU or DDU,
- b. Fibrinogen level change from baseline to Day 9 in mg/dL
- c. Prothrombin time change from baseline to Day 9 in seconds
- d. Length of hospital stay in days,
- e. Mortality (%) of overall and between groups,
- f. Pulmonary function
  - a. Time (days) to mechanical ventilation and/or
  - b. ECMO Duration (days) or extracorporeal membrane oxygenation (ECMO) use,
- g. SOFA score change from baseline to Day 9 and
- h. SOFA Respiratory sub-score change from baseline to Day 9,
- i. Number of venous thromboembolisms from admission to hospital discharge,
- j. Number of major bleeding events from admission to hospital discharge

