Thus, COVID might be a dysregulated inflammatory state superimposed on disseminated intravascular coagulation (DIC) with consumptive coagulopathy [PMID: 32302438]. These patients are at high risk for both thrombosis and bleeding, as well as an overwhelming cytokine storm. The pathogenic mechanism is not fully elucidated, but the dysregulated coagulation is probably orchestrated by inflammatory cytokines, lymphocyte cell-death, hypoxia, and endothelial damage [PMID: 32558075]. This is a project to develop an entirely novel evidence-based treatment that targets both the coagulopathy and the inflammation.

In 183 consecutive patients with COVID, the overall mortality was 11.5%. On admission, the non-survivors had higher D-dimer and fibrin degradation product (FDP) levels, longer prothrombin time and activated partial thromboplastin time compared to survivors; 71.4% of the deaths and only 0.6% survivors met the criteria of DIC [PMID: 32073213]

In 40 patients with COVID, whole blood thromboelastometry (TEM) was consistent with hypercoagulability characterized by an acceleration of blood clot formation and higher clot strength. This hypercoagulable state persists for at least 5-10 days and was associated with deep vein thrombosis in six patients (15%), thromboembolism in 2 patients (5%), and catheter-related thrombosis in 12 patients (30%). The ICU and the hospital mortality were 10% and 12.5%, respectively. [PMID: 32394236]

In 16 COVID patients, the pro-coagulant TEM profile was characterized by an increased clot strength (CS), platelet contribution to CS, fibrinogen contribution to CS elevated D-dimer levels, and hyperfibrinogenemia. Fibrinogen levels were associated with interleukin-6 values. [PMID: 32302448].

In 24 COVID patients, the R, K, Alpha, and MA TEM parameters were all consistent with hypercoagulability. Platelet count was normal or increased, prothrombin time and activated partial thromboplastin time were near normal. Fibrinogen, D-dimer, C-reactive protein, Factor VIII and von Willebrand factor, protein C were all increased whereas AT3 was decreased [PMID: 32302438]. In 94 patients with COVID vs 40 healthy controls, whereas D-dimer, fibrin/fibrinogen degradation products (FDP), and fibrinogen (FIB) in all SARS-CoV-2 cases were all higher, but AT3 was lower [PMID: 32172226].

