**7) Study Endpoints\***

The Primary endpoint is change from baseline in the ISTH DIC Score to Day 9.

The Secondary endpoints include change from baseline D-dimers, Fibrinogen & Prothrombin time, length of hospital stay (days), mortality (%), and Pulmonary function (including Time (days) to mechanical ventilation and/or ECMO Duration (days) of new ventilator or extracorporeal membrane oxygenation (ECMO) use, Change from baseline SOFA and SOFA Respiratory sub-score, Number of venous thromboembolisms, Number of major bleeding events

Subjects discharged prior to completion of intervention would be classified as having a successful outcome. We anticipate that all cause morbidity will occur in 10-20% of the COVID study population, despite standard of care. We anticipate that these patients will be deficient in endogenous AT3.

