## **9) Statistics\***

Statistical analyses will be performed using SPSS version 21 (IBM Corporation, Armonk, NY). Parametric data are reported as  $M \pm SD$  and nonparametric data are reported as median (interquartile range). Missing values for continuous variables are handled by applying imputation methods before calculating their statistics. The study population will be stratified into two halves based on the primary outcome of change from baseline SOFA and/or ICH DC. Those with the fastest rate of recovery are compared to those with the slowest rate of recovery. We expect that AT3 will correlate with rate of recovery and/or with one or more of the secondary outcomes. The demographics and physiologic variables in the fastest and slowest groups are compared using a t test or Mann-Whitney U-test, as appropriate. Categorical variables are compared using a  $\chi^2$  or Fisher's exact test, as appropriate. Statistical significance is determined at  $p < 0.05$ . Then multivariate models will be evaluated for predicting the primary or secondary outcomes, using various performance metrics, such as area under the receiver operating characteristic curve, sensitivity and specificity, positive predictive value, and negative predictive value, as we have described in multiple previous studies. In addition, propensity scores will be assigned for each patient based on a 1:1 fixed ratio nearest neighbor matching was performed to compare those with fastest or slowest recovery. A 1:1 fixed ratio nearest neighbor matching is performed to minimize bias without sacrificing power, as we have described in multiple previous studies.

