### **List of Expected Adverse Events**

Acute respiratory failure; respiratory distress; acute lung injury; acute respiratory distress syndrome (ARDS); acute renal failure; coagulation dysfunction; decreased platelets count; neutropenia; hypothermia; fever, bacteremia; sepsis, septic shock; hypotension; metabolic acidosis, pleural effusion; abdominal compartment syndrome; repeated surgeries/debridement; amputation.

For purposes of this study, deaths will be captured as clinical outcomes and do not need to be reported as SAEs unless felt related to study drug administration.

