### **11) Withdrawal of Subjects\***

The occurrence of any of the following events may necessitate premature withdrawal of a subject from the study:

- Development of any of the following Inclusion/Exclusion criteria:
  - Subjects with a "do not resuscitate" order,
  - Multi-organ failure,
  - History of hypersensitivity or allergy to any component of the study drug,
  - Ongoing massive surgical or unexplained bleeding,
  - History of bleeding or clotting disorder,
- Occurrence of a serious adverse event (SAE) thought to be related to study drug and not alleviated by symptomatic treatment
- Unwillingness to continue in the clinical study
- Death of the subject
- Principal Investigator decision (i.e. subject non-compliance with study procedures)
- Significant AE or medical decision that precludes the subject from adhering to study requirements

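### Length of stay in raw days does not separate in-hospital death from live discharge, so the comparison mixes recovery with mortality, in a direction set by when deaths occur

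*Combined protocol and SAP*

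**What the plan says.** Section 7 lists the endpoint as "length of hospital stay (days), mortality" and Appendix C, item d, repeats it as "Length of hospital stay in days". The Appendix B flowsheet collects it on discharge. Neither definition says what value a patient who dies in hospital receives.

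Death appears in four other places, none linked to length of stay:

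- Appendix C, item e, makes it a separate endpoint: "Mortality (%) of overall and between groups".
- The list of expected adverse events in Section 10 says that "deaths will be captured as clinical outcomes and do not need to be reported as SAEs unless felt related to study drug administration".
- Section 11 lists "Death of the subject" among events that may lead to withdrawal, with no consequence for any endpoint.
- Appendix B collects mortality in the same column as length of stay.

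Section 9 applies unspecified imputation to missing continuous values. It says that demographic and physiologic variables are "compared using a t test or Mann-Whitney U-test, as appropriate", but the groups compared there are the fastest and slowest to recover, not the treatment arms. It names no time-to-event or competing-risk method.

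**The concern.** A stay that ends in death on Day 3 and a stay that ends in recovery on Day 12 are both plain day counts, and the first is the smaller number. A patient who dies has an observed count, so nothing is missing and the imputation sentence does not apply. If shorter is read as better, a difference in mortality between groups feeds directly into the length-of-stay comparison.

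Deaths should be expected. Section 2 cites a 40-patient series in which "The ICU and the hospital mortality were 10% and 12.5%, respectively", and a 183-patient series with 11.5% overall mortality. Section 3 excludes patients expected to die within 24 hours, those with a do-not-resuscitate order, and some other high-risk groups, but later deaths remain possible. At stake is whether a difference in mean or median stay can be interpreted at all, since it could reflect faster recovery, more early deaths, or both.

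**Working it through.** The documents give no effect size, standard deviation, power, survivor stay or timing of death for this endpoint, so there is no figure of the plan's to reproduce. What follows is an illustration with assumed inputs.

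**Inputs from the documents**
- Randomised comparison: 25 versus 25 (Section 4).
- Hospital mortality in one cited series: 12.5% (Section 2), so about 0.125 × 25 = 3.1 deaths per arm.

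**Assumptions**
- Survivor stay is identical in both arms: lognormal, median 12 days, log-SD 0.6. Its mean is 12 × exp(0.6²/2) = 12 × exp(0.18) = 14.37 days.
- Mortality is 12.5% in one arm and 25% in the other. The 25% is not in the documents.
- Day of death is uniform over a window, which is varied.

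**Formula.** With mortality p, mean raw stay = (1 − p) × survivor mean + p × mean day of death. The difference (more deaths minus fewer) is therefore

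(0.25 − 0.125) × (mean day of death − 14.37).

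The share of trials in which the higher-mortality arm has the shorter mean stay comes from 40,000 simulated trials per row.

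| Deaths on Days | Mean day of death | Shift in mean stay, days | Higher-mortality arm looks better |
|---|---|---|---|
| 2-10 | 6 | 0.125 × (6 − 14.37) = −1.05 | 66% |
| 5-20 | 12.5 | 0.125 × (12.5 − 14.37) = −0.23 | 54% |
| 4-24 | 14 | 0.125 × (14 − 14.37) = −0.05 | 51% |
| 8-30 | 19 | 0.125 × (19 − 14.37) = +0.58 | 41% |

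With equal mortality of 12.5% the share is 50%. The between-arm difference in mean stay has a standard deviation of about 2.6 days across trials, so even the −1.05-day shift is well under one standard deviation.

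**A larger imbalance.** At 10% versus 30% mortality with deaths on Days 2-10, the shift is 0.20 × (6 − 14.37) = −1.67 days, and the higher-mortality arm looks better in 74% of trials.

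**If a Mann-Whitney test on raw days were used between arms** (two-sided 5%, deaths on Days 2-10, 4,000 trials per scenario), it would be significant in favour of the arm with more deaths in about 7% of trials at 12.5% versus 25%, and about 13% at 10% versus 30%. The nominal rate in that direction is 2.5%. With in-hospital deaths ranked worst, these fall to about 0.2% and 0.05%.

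**A second set of assumptions.** With mean survivor stay of 10 to 20 days, death on Day 3 to 7, and mortality of 12% versus 24% or 10% versus 20%, the arm with more deaths appears 0.3 to 2.0 days better. If the mean day of death equals the survivors' mean stay, the shift is zero. If deaths come 6 days later than that mean, it is +0.6 to +0.7 days.

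**The case against.** The strongest reply is that the harmful direction is an assumption. The documents give no timing of death, and patients who die after long intensive care would lengthen the mean stay of their arm. This stands. The table shows a shift that goes from about a day in one direction to more than half a day in the other.

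Second, the Section 9 sentence on the t test and Mann-Whitney test concerns fast versus slow recoverers. A reader might infer that the plan prescribes a biased between-arm test of length of stay. It does not; it names no such test. This stands too, although it leaves the endpoint with less specification rather than more.

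Third, Section 7 states "Subjects discharged prior to completion of intervention would be classified as having a successful outcome". A reader might take this to mean that a short stay ending in death counts as success. The sentence concerns discharge, does not mention death and assigns no length-of-stay value, so it does not support that reading.

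Fourth, the plan never says outright that a death is scored as a short stay. That is true. It follows from applying a plain day count with no exception, and an analyst could depart from it by excluding deaths, but the plan provides no rule for doing so.

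Finally, mortality is reported between groups, so a gross imbalance would be visible. That helps a reader notice the problem. It does not correct the length-of-stay estimate or any p-value attached to it.

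**Conclusion.** The point holds in a limited form. Length of stay, as defined, combines two outcomes with opposite clinical meaning, and the plan has no rule to separate them. In the illustration, doubling mortality from 12.5% to 25% moves mean stay by between −1.0 and +0.6 days depending only on when deaths occur, with identical recovery among survivors. The size rests on the assumed survivor distribution, the assumed mortality contrast and the assumed death windows.

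The documents do not support the stronger conclusion that the endpoint will favour a harmful arm. That needs both unequal mortality and deaths earlier than survivors' discharge, and neither can be established from the text. Because the direction cannot be known beforehand, the rule should be fixed before the data are analysed. The matter is confined to one secondary endpoint of an open-label pilot. The primary endpoint, change in ISTH DIC score to Day 9, is not affected by this point.

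**What to change.** In Appendix C, item d, and in Section 9, specify one of the following for the comparison of the two randomised arms:

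- time from randomisation to discharge alive, with in-hospital death as a competing event, summarised by cumulative incidence; or
- a Mann-Whitney comparison of length of stay with all in-hospital deaths ranked worse than any live discharge.

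Report raw days in survivors descriptively only, since survivors are a subset selected after randomisation. Confirm that the date of death is captured: Appendix B lists mortality and length of stay on discharge but does not name that date.

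The cost is a few sentences of analysis text and possibly one field on the case report form. Visits, sample size and treatment are unchanged. The small downside is that either result is less intuitive than a difference in mean days.

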**8) Procedures Involved\***

Any member of the study team will discuss potential subjects with the clinical team for appropriate pursuit of informed consent and screening for eligibility.

75 eligible subjects, after consent, will have laboratory blood tests for further screening.

25 of those subjects with endogenous **AT3  $\geq$  100%** will continue with SOC.

50 of those subjects with endogenous **AT3 < 100%** will be will be randomly assigned to begin **SOC plus treatment with exogenous AT3 supplementation or only SOC** treatment. The randomization schedule will be established by a member of the study team that is not involved in the informed consent process.

They will all be followed up for laboratory blood tests, study endpoints and adverse events. If they do not meet entry criteria they will be excluded from the study.

[figure not shown]
Consented subjects will be scored according to The International Society of Thrombosis and Haemostasis Disseminated Intravascular Coagulation scale (ISTH DIC) on study visit days 1, 3, 5, 7, 9 and 11.

The SOFA score will be performed only when the parameter is obtained clinically and monitored for changes in patient status on study visit days 1, 3, 5, 7, 9 and 11. Each organ system is assigned a point value from 0 (normal) to 4 (high degree of dysfunction/failure). It will be calculated on admission and Day 11 using the worst parameters measured during the study visit day. If a parameter is not obtained clinically it will be voided for research purposes.

UM IRB# 20201048

AT3 in COVID-19  
January 24, 2022, Version 6.2

After enrollment and each 48h period (+/- 12 hours) thereafter, blood samples are collected and assayed for routine clinical coagulation and inflammation markers, including AT3 activity, D-Dimer, anti-Xa, fibrinogen, and prothrombin time until Day 11.

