### Dosing Rationale-

In those COVID(+) patients with an endogenous AT3 activity level <100% and at the discretion of the attending physician, Day 1 infusion of AT3 will be at a dose to be adjusted based on initial body weight up to 100 kg maximum and to a set target plasma activity level of 120% according to the following formula:

$$= \frac{(120\% - \text{baseline AT3}\%)}{1.4} \times \text{body weight (kg)}$$

Based on an example of an 85kg patient with a baseline AT activity level of 90%,

- The dose would be 1,821 units on a dosing schedule of Day 1, 3, 5, 7 & 9
- For a total of approximately 9100 units
- Each Thrombate III vial contains 500 units each reconstituted with 10 mL of Sterile Water for Injection, USP, the final concentration is approximately 50 units per mL.
- Requiring 4 vials per dose or 20 vials per patient

Each 85kg patient will receive ~9100 IU's over 5 doses requiring 20 vials

- (10% overage to account for any dose adjustments needed)
- therefore each patient would require 10,000 IU's
- for a total of 250,000 IU's or 500 vials for the study.

AT3 will be drawn every other day, pre-dose, for monitoring, and verification of 120% target plasma activity level. Dosing schedule will be as follows: Day 1, 3, 5, 7 & 9 a dose will be given if AT3 activity level remains less than 100% on those days, otherwise no dose will be given. Days refer to a 24 hour period.

Data to be collected from the medical record according to the Study Flowsheet (Appendix B) will include:

- a. Demographics: age, comorbidities, medical history, concomitant meds, vital signs, height and weight,
- b. ISTH DIC score and a Sofa Score,
- c. Laboratory values:
  - a. Platelets, PT, INR, PTT, D-Dimer, Fibrinogen, AT3 level, Anti-Xa,
- d. Outcomes:
  - a. Length of Stay, Mortality, change in PF ratio, Vent/ECMO days, # and severity VTE's, # and severity of bleeding events

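### SOFA endpoints g and h are defined at Day 9, but the flowsheet schedules SOFA only on Day 1 and Day 11, and Section 8 is inconsistent about Day 9

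*Combined protocol and SAP*

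**What the plan says.** Appendix C sets the day for both SOFA endpoints. Item g is "SOFA score change from baseline to Day 9 and" (the last word leads into the next item), and item h is "SOFA Respiratory sub-score change from baseline to Day 9".

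Appendix B marks the SOFA row under Enrollment - Day 1 and under Day 11. The cell under the combined column for Days 3, 5, 7 and 9 is blank. The row for "ISTH DIC Score" directly above it is marked in all three of those columns. The flowsheet is more than an illustration: the data list at the end of Section 8, which includes the SOFA score, opens with "Data to be collected from the medical record according to the Study Flowsheet (Appendix B) will include".

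Section 8 makes two statements about SOFA in one paragraph. The first has SOFA performed solely where clinical care supplies the inputs; scores are also to be "monitored for changes in patient status on study visit days 1, 3, 5, 7, 9 and 11". Then: "It will be calculated on admission and Day 11 using the worst parameters measured during the study visit day".

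Section 7 lists change from baseline in SOFA and its respiratory sub-score as secondary endpoints, without a day. Section 9 names SOFA change, and/or an abbreviation that is presumably the ISTH DIC score, as the primary outcome used to split the population into faster and slower recovery. It gives no day either.

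**The concern.** An endpoint defined at a visit where its score is neither scheduled nor calculated cannot be produced by following the schedule. Staff working from the flowsheet would deliver SOFA scores for Day 1 and Day 11. The analyst would then have to rebuild a Day 9 score from the chart or substitute the Day 11 score, and in an open-label trial that decision should be made in advance.

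The two days are not interchangeable. Day 9 is the last listed dosing day and Day 11 comes after it. A patient who dies or is discharged between the two can have a Day 9 score and no Day 11 score. Section 9 brings SOFA change into its statement of the primary outcome, so the missing day may also affect the split on which that section's comparisons rest.

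The baseline is loose as well. Section 8 says admission and the flowsheet says enrolment Day 1. Section 5 recruits patients who are already inpatients, so the two may be different days.

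**Working it through.** The plan gives no figure to reproduce. The check sets the passages side by side.

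**SOFA days by source**

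- Appendix C, items g and h: baseline and Day 9.
- Appendix B, SOFA row: Day 1 and Day 11.
- Section 8, calculation sentence: admission and Day 11.
- Section 8, performed-and-monitored sentence: Days 1, 3, 5, 7, 9 and 11, when obtained clinically.
- Section 7 and Section 9: change from baseline, no day.

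Appendix C and Appendix B share only the baseline. The blank cell is unlikely to be a conversion fault: the neighbouring rows keep their marks in that column, and the Section 8 calculation sentence names Day 11 independently.

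**How many Day 9 endpoints are affected**

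- Change endpoints set at Day 9: the Section 7 primary (ISTH DIC) plus Appendix C items a (D-dimer), b (fibrinogen), c (prothrombin time), g and h: 1 + 5 = 6.
- Marked in the flowsheet column that contains Day 9: ISTH DIC, D-dimer, fibrinogen and prothrombin time: 4.
- Not marked: 6 − 4 = 2, both SOFA. Among the secondary endpoints set at Day 9 this is 2 of 5.

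**Which Day 9 inputs exist anyway**

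SOFA as set out in Appendix A has six organ systems. The flowsheet column containing Day 9 marks platelets, and vital signs and concomitant medications. These would serve the hematologic item and, assuming blood pressure is among the vital signs, the cardiovascular item. The flowsheet has no row for bilirubin, creatinine or the Glasgow Coma Score, and it lists PF ratio change only at discharge. Those inputs would have to come from the chart if they were obtained clinically. The Day 9 score is therefore partly supported and not scheduled.

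**Distance to the nearest scheduled score**

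- Interval as defined: 9 − 1 = 8 days.
- Interval as scheduled: 11 − 1 = 10 days, which is 2 days longer.

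**Whether a visit window bridges the gap**

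The only window is for blood: "After enrollment and each 48h period (+/- 12 hours) thereafter, blood samples are collected". Applying it to SOFA is an assumption, and its anchor is not stated.

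- Anchored to enrolment: a Day 9 visit up to 12 h late and a Day 11 visit up to 12 h early are still 48 − 12 − 12 = 24 h apart.
- Anchored to the preceding draw: Day 9 is the fourth 48 h interval and could run 4 × 12 = 48 h late, which is nominal Day 11.

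The window therefore settles nothing in either direction.

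**The case against.** The best defence is that the endpoint is clear. Appendix C fixes Day 9 for both items and no endpoint definition says Day 11, so there are not two rival endpoints. Section 8 has SOFA performed and monitored on Day 9 when the parameters are obtained clinically, and some inputs are scheduled that day. An analyst could take Appendix C at its word and build the score from the chart.

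Much of this stands. A reader might infer that Section 8 restricts SOFA to baseline and Day 11. It does not: that restriction is exact for the flowsheet row and for the calculation sentence, but the sentence before the latter includes Day 9. A reader might also infer that Day 9 SOFA data are lost. The documents do not show that, because clinically obtained values could still be abstracted.

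The defence does not remove the contradiction. The sentence that includes Day 9 is followed by one naming only admission and Day 11 for the calculation, and the flowsheet that governs collection agrees with the second. Someone following the schedule has no instruction to produce the score that items g and h need.

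**Conclusion.** The contradiction is real and should be corrected. Two of the six change endpoints set at Day 9, both SOFA, have no scheduled score that day, and Section 8 gives conflicting accounts of whether there should be one. The effect on results cannot be sized: the documents do not say how many patients would die or be discharged between Day 9 and Day 11, or how often the unscheduled SOFA inputs would be in the chart.

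Three further inferences go beyond the documents.

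- That a Day 11 score can never pass as a late Day 9 score. This borrows a window written for blood samples and assumes that it is anchored to enrolment.
- That the problem is confined to secondary endpoints. Section 9 places SOFA change in the primary outcome, so this cannot be asserted.
- That the primary endpoint cannot be measured. Section 7 defines it as ISTH DIC change to Day 9, and the flowsheet schedules that assessment.

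The conclusion rests on reading the blank flowsheet cell as intended, which the Section 8 calculation sentence supports.

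**What to change.** Reconcile Sections 7, 8 and 9 and Appendices B and C to one SOFA day, and name enrolment Day 1 as the baseline in place of admission. Either of two changes does this.

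1. **Keep Day 9.** Add a Day 9 SOFA score to the flowsheet by chart abstraction, with no new tests, and amend the Section 8 calculation sentence to match. Split or footnote the combined column so that only Day 9 is added. The cost is at most 75 × 1 = 75 abstracted scores; marking the whole combined column would raise this to as many as 75 × 4 = 300. The SOFA endpoints then fall on the same day as the primary endpoint and Appendix C items a to c.
2. **Move to Day 11.** Redefine items g and h at Day 11. This adds no scores. The SOFA endpoints then fall on a different day from the primary endpoint and may lose patients who die or are discharged between Day 9 and Day 11.

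Whichever is chosen, state the day wherever Sections 7 and 9 mention SOFA change, and settle in Section 9 whether SOFA belongs to the primary outcome. The rest of the cost is a wording amendment.
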